Name of Sponsor: InFlectis BioScience	Protocol ID or Number P188	Name of Investigational product: IFB-088 Oral capsule	Name of active ingredients: IFB-088
Title of Study	A double-blind, randomized, placebo-controlled, combined single and multiple ascending dose study to investigate the safety, tolerability and pharmacokinetic profile of IFB-088, in healthy volunteers		
Principal Investigators	SAD: Dr [name]	Study center CIC-CP CET Hôpital de la Timone- Assistance Publique des Hôpitaux de Marseille	
	MAD: Dr [name]	Eurofins Optimed [name]	
Phase of development	Phase I		
Rationale	This is the first study of single and multiple doses of IFB-088 in human subjects. The current study is designed to assess in the first part, the safety, tolerability, plasma and urine pharmacokinetics (PK) of single oral doses of IFB-088 in healthy subjects (SAD) and in a second part safety, tolerability, plasma and urine pharmacokinetics (PK) of multiple oral doses of IFB-088 in healthy subjects (MAD)		
Objectives	
Primary
 
To investigate the safety and tolerability of IFB-088 after single and multiple oral doses in healthy volunteers
 
Secondary
 
To investigate the pharmacokinetics of IFB-088 after single and multiple oral doses in healthy volunteers
		
Study Design	
Randomized, double blind, placebo controlled study of single ascending doses (SAD) and multiple ascending doses (MAD)
 
The SAD part consists of 6 cohorts of 8 healthy young male subjects, each receiving a single oral dose of IFB-088 or placebo (6 verum and 2 placebo). In each cohort, 2 subjects (1 verum and 1 placebo) will be dosed first. If the safety and tolerability results are acceptable, the 6 remaining subjects will be dosed by 2 successive groups of 3 subjects, with an adequate period between the 2 groups to detect the occurrence of any reaction or adverse events, namely at least 48H for the first cohort and at least 36H for the following cohorts. Indeed, in the first cohort (2.5 mg IFB-088 base), dosing will be in the morning only. From the second cohort, the planned daily dose will be divided into 2 doses separated by an interval of 12 hours (1 dose in the morning fasting and 1 dose in the evening 2 hours before dinner).
 
The MAD part consists of 3 cohorts of 8 healthy young male subjects, each receiving an oral dose divided into two doses of IFB-088 or placebo (6 verum and 2 placebo) for 14 days. In each cohort, the 2 first subjects will be dosed on Day 1 (one on active treatment and one on placebo). The 6 remaining subjects will be dosed by 2 successive groups of maximum 3 subjects with an adequate period between the groups to observe for any reaction and adverse events. This period will be of at least 36H, corresponding to at least 5-fold the half-life of the drug (based on results obtained during the SAD part) when steady state will be achieved. In each MAD cohort, the total daily dose will be divided into 2 doses separated by an interval of 12 hours.
		

Number of subjects	Seventy-two (72) healthy young subjects (48 in the SAD part and 24 in the MAD part)												
Test product, dose and mode of administration	
  
 Name	Pharmaceutical Form	Unit dose strength	Mode of administration	
   
 IFB-088	Capsules	2.5 to 30 mg	Oral	
 
 Placebo	Capsules	NA	Oral	
  
 
SAD
 
Cohort 1: A single dose of 2.5 mg IFB-088 oral capsule (n=6) or matching placebo (n=2) on D1
 
Cohort 2: A single daily dose of 5 mg of IFB-088 oral capsule (n=6) or matching placebo (n=2) divided into 2 doses of 2.5 mg separated by an interval of 12 hours on D1.
 
Cohort 3: A single daily dose of 10 mg IFB-088 oral capsule (n=6) or matching placebo (n=2) divided into 2 doses of 5 mg separated by an interval of 12 hours on D1
 
Cohort 4: A single daily dose of 20 mg IFB-088 oral capsule (n=6) or matching placebo (n=2) divided into 2 doses of 10 mg separated by an interval of 12 hours on D1
 
Cohort 5: A single daily dose of 40 mg IFB-088 oral capsule (n=6) or matching placebo (n=2) divided into 2 doses of 20 mg separated by an interval of 12 hours on D1
 
Cohort 6: A single daily dose of 60 mg IFB-088 oral capsule (n=6) or matching placebo (n=2) divided into 2 doses of 30 mg separated by an interval of 12 hours on D1
 
Escalation to the next higher dose and any dose adjustments of the next dose levels will be based on safety and tolerability results of the previously administered dose and PK data of the previous dose cohorts. There will be a 2-fold increase from the first dose level (2.5 mg) to the second dose level. The dose levels of the following groups will be increased by 2-fold from the previous dose level from cohort 3 to cohort 5 and 1.5-fold from cohort 5 to the last cohort.
 
MAD
 
Cohort 1: A daily dose of 15 mg of IFB-088 oral capsule (n=6) or matching placebo (n=2), divided into 2 doses of 7.5 mg, separated by an interval of 12 hours from D1 to D14
 
Cohort 2: A daily dose of 30 mg of IFB-088 oral capsule (n=6) or matching placebo (n=2), divided into 2 doses of 15 mg, separated by an interval of 12 hours from D1 to D14
 
Cohort 3: A daily dose of 50 mg of IFB-088 oral capsule (n=6) or matching placebo (n=2), divided into 2 doses of 25 mg, separated by an interval of 12 hours from D1 to D14
 
Escalation to the next higher dose and any dose adjustments of the next dose levels will be based on safety, tolerability and PK results of the previously administered dose.
	Name	Pharmaceutical Form	Unit dose strength	Mode of administration	IFB-088	Capsules	2.5 to 30 mg	Oral	Placebo	Capsules	NA	Oral
Name	Pharmaceutical Form	Unit dose strength	Mode of administration										
IFB-088	Capsules	2.5 to 30 mg	Oral										
Placebo	Capsules	NA	Oral										
Inclusion criteria	
Subjects must satisfy all of the following inclusion criteria:
 
 
1. Healthy male 18 to 40 years of age inclusive, Caucasian. 
2. Healthy as determined by a responsible and experienced physician, based on a medical evaluation including medical history, physical examination, laboratory tests, vital signs and ECG. 
3. AST, ALT, alkaline phosphatase and bilirubin $\leq 1.5 \times \text{ULN}$ (isolated bilirubin $> 1.5 \times \text{ULN}$ is acceptable if bilirubin is fractionated and direct bilirubin $< 35\%$). 
4. ECG (12 leads) normal ($120 < \text{PR} < 200 \text{ms}$; $\text{QRS} < 120 \text{ms}$; $\text{QTcF} < 450 \text{ms}$) and/or without clinically relevant impairments as judged by investigator. 												

	
 5. Non-smoker or user of not more than tobacco- or nicotine-containing products ≤ 5 cigarettes a day. 6. Negative screen for alcohol and drugs of abuse at screening and admission. 7. No history of psychiatric disorders assessed by a clinical psychological evaluation and the Mini International Neuropsychiatric Interview (MINI). 8. Body mass index (BMI) between 19 and 27 kg/m² inclusive. 9. Subject with female partners of child bearing potential must agree to use one of the contraception methods listed in Section 6.6.1 (Contraception requirements). This criterion must be followed from the time of the first dose of study medication until the follow up visit (for female partners) and with an additional period of 90 days (for subjects themselves). 10. Willing and able to understand and sign an approved Informed Consent Form. 11. Able to understand the protocol and to come to the visits. 12. Who is, in the judgement of the investigator likely to be compliant during the study. 13. Subject registered in the VRB file (volontaires se prêtant à des recherches impliquant la personne humaine). 14. Covered by Health Insurance System and / or in compliance with the recommendations of National Law in force relating to biomedical research.

Exclusion criteria
	
A subject will not be eligible for inclusion in this study if any of the following criteria apply:
 
 1. History of asthma, anaphylaxis or anaphylactoid reactions, severe allergic responses. 2. History of relevant atopy or drug hypersensitivity. 3. Known allergy to any component of IFB-088 oral capsule or its placebo (HPMC or cellulose microcrystalline). 4. History of major medical, psychiatric illness or surgery which, in the judgment of the investigator, puts them 'at risk' or is likely to modify their handling of the study drug. 5. Acute or chronic systemic disease or disorder (respiratory, gastrointestinal, renal, hepatic, haematological, lymphatic, neurological, cardiovascular, psychiatric, musculoskeletal, genitourinary, immunological, dermatological, endocrine). 6. Impaired renal function defined by a creatinine clearance < 90 mL/min calculated using the Cockcroft-Gault equation (according the FDA Guidance for Industry: Pharmacokinetics in patients with Impaired Renal Function, March 2010). 7. History of nephritic colic and/or renal calculi. 8. History of drug abuse and/or regular use of tobacco- or nicotine-containing products > 5/day within three months of the study. 9. History of alcohol consumption exceeding, (on average 21 drinks/week for men) within 6 months of the first dose of study medication. 10. Drinking excessive amounts of tea, coffee, chocolate and/or beverage containing caffeine (> 4 cups / day). 11. Vital signs with a clinically significant abnormality at screening. 12. ECG with a clinically significant abnormality at screening. 13. Laboratory test values outside the clinically acceptable 'normal range' for healthy volunteers at screening. 14. Positive HIV, Hepatitis B or Hepatitis C at screening. 15. Positive urine drug test or positive breath alcohol test at screening or at admission to the clinical unit. 16. Any medication (including St John's Wort) within 14 days before administration, or within 5 times the elimination half-life of that drug, whichever is the longest (except paracetamol). 17. Treatment with an investigational drug within 30 days or 5 half-lives (whichever is longer) prior to screening. 18. Unable to refrain from consumption of grapefruit or grapefruit juice within 7 days prior to the first dose of study medication.

	
19. Unwillingness to abstain from sexual intercourse with pregnant or lactating women or to use a condom and spermicide and another form of contraception (e.g., IUD, birth control pills taken by female partner, diaphragm with spermicide) if engaging in sexual intercourse with a woman who could become pregnant until discharge from the study and during 90 additional days.
 
20. Subjects unlikely to co-operate in the study, and/or poor compliance anticipated by the investigator.
 
21. Subject being in the exclusion period of a previous trial.
 
22. Subject having exceeded the earnings for the last 12 months, including the indemnities for the present study.
 
23. Subject who could not be contacted in case of emergency.
 
24. Subject refusing to give written informed consent.
 
25. Subject who has received blood or plasma derivatives in the year preceding the study.
 
26. Subject who has given blood within the past 3 months or has planned to give blood or sperm within the 90 days following the study.
 
27. Subject who has forfeited their freedom by administrative or legal award, or who is under guardianship or under limited judicial protection.

Concomitant medications and study restrictions
	
Subjects must abstain from taking prescription or non-prescription drugs (including vitamins and dietary or herbal supplements), within 14 days or 5 half-lives (whichever is longer) prior to the first dose of study medication until completion of the follow-up visit. Occasional use of paracetamol at doses up to 2 grams/day will be permitted at the principal investigator's discretion.
 
Subjects will abstain from alcohol-, caffeine- or xanthine-containing beverages (e.g. coffee, tea, cola drinks, chocolate) for 24 hours prior to the start of dosing until collection of the final PK sample during each session. Subjects will abstain from grapefruit or grapefruit-containing products for 7 days prior to the first dosing until follow-up visit and from strenuous exercise for 48 hours prior to each blood collection for clinical laboratory tests.


Procedures
	
Screening
 
Subjects will be screened for eligibility between D-21 and D-2 before the first study drug administration. Written informed consent will be obtained before any study procedure. The screening will consist of: medical history, full physical examination (including height and body weight), vital signs (supine and standing systolic and diastolic blood pressure, pulse rate and tympanic body temperature), 12-lead ECG, haematology, coagulation, plasma biochemistry and urinalysis tests, viral serology testing (hepatitis B antigen, Hepatitis C antibodies, Anti-HIV1 and Anti HIV2 antibodies), drugs of abuse and alcohol screen, psychological interview and review of the eligibility criteria.
 
The results of screening must be known to the investigator prior to the subject's admission.
 
Admission
 
Subjects will be admitted to the clinical unit one day prior to dosing (D-1) to undergo the following assessments:
 
 • Medical history and physical examination update, • Vital signs measurement (including tympanic body temperature), • 12-lead ECG, • Laboratory evaluation (haematology, coagulation, biochemistry, urinalysis), • Urine drug screen, • Alcohol breath test, • AE monitoring,

	
 • Review of concomitant medications, • Verification of the eligibility criteria, • Randomization to the treatment group after check of all criteria. 
The results of admission assessments must be known by the investigator prior to the subjects dosing.
 
Hospitalization period
 
◆ SAD
 
Subjects will be required to stay in the unit for up to 2 nights for the treatment period from Day-1 to Day 2. Subjects will be dosed on Day 1 and will be discharged after completion of all assessments and with medical authorization at Day 2, 32 hours after first dosing.
 
◆ MAD
 
Subjects will be required to attend the unit on the day (Day -1) prior to the first dose and to stay in the unit for 17 days. Subjects will be dosed from Day 1 to Day 14 and will be discharged after completion of all assessments and with medical authorization at Day 17.
 
Follow-up (FU)
 
Subjects will be required to return to the unit for a follow-up visit between 7 days and 14 days after last dosing or early discontinuation, for safety assessments: physical examination; vital signs (supine and standing systolic and diastolic blood pressure, pulse rate and tympanic body temperature), 12-lead ECG, haematology, coagulation, plasma biochemistry and urinalysis tests.


Evaluation criteria
	
Safety assessments
 
◆ SAD
 
 • Adverse events (AEs): throughout the study period i.e. from screening to follow-up visit • Full physical examination at screening, discharge and FU and physical examination update at Day-1 and throughout the study on medical indication at the discretion of the investigator • Supine and standing vital signs: on D-1; D1 at pre-dose (in triplicate), and 0.5, 1, 2, 3, 4, 6, 8, 12, 24 and 32h post dose; FU • Tympanic body temperature: on D-1; D1 pre-dose; and 1.5, 12, 24 and 32h post dose; FU • ECG on D-1; D1 at pre-dose (in triplicate) and 1, 2, 4, 8, 12, 24 and 32h post dose; FU • Laboratory evaluation: haematology, coagulation and biochemistry on D-1, D2 24h post dose and FU; urinalysis on D-1; D1 at pre-dose and 12h, 24h and 32h post dose; FU • Vigilance (Bond and Lader VAS) on D1 pre-dose and 1.5, 12 and 32h post dose 
◆ MAD
 
 • Adverse events (AEs): throughout the all study period i.e. from screening to follow-up visit • Full physical examination at screening, discharge and FU and physical examination update at Day-1, D3, D6, D10 and D13 before morning dose and throughout the study on medical indication at the discretion of the investigator; • Supine and standing vital signs: on D-1; D1 at pre-dose (in triplicate), and 0.5, 1, 2, 3, 4, 6, 8, 12 post first dose; D2 24h post first dose; every morning pre dose from D3 to D17; FU

	
• Tympanic body temperature: on D-1; D1 pre-dose, 1.5 and 12h post first dose; on D2, D4, D6, D8, D10 and D12 every morning before dosing; on D14 at pre dose, and 1.5, 12h post dose; on D17 before discharge; FU• ECG on D-1; D1 at pre-dose (in triplicate) and 1, 2, 4, 8, 12h post first dose; D3, D6, D10 and D13 in the morning before dosing and D17 at discharge; FU• Laboratory evaluation: haematology, coagulation and biochemistry on D-1, D3, D6, D10 and D13 in the morning before dosing and D17 at discharge; FU; urinalysis on D-1; D1 at pre-dose, D3, D6, D10 and D13 in the morning before dosing and D17 at discharge; FU• Vigilance (Bond and Lader VAS) on D1 pre-dose and 1.5, 12h post dose; on D14 pre dose and 1.5, 12h post dose 
Pharmacokinetic Assessments in blood
 
◆ SAD
 
First cohort (dosing in the morning): blood sampling for PK of IFB-088 and its metabolite at pre-dose and 0.16, 0.33, 0.5, 0.75, 1, 1.5, 2, 2.5, 3, 4, 5, 8, 12, 24 and 32h post dose
 
From Cohort 2 (daily dose separated in 2 administrations with a 12-hour interval): blood sampling for PK of IFB-088 and its metabolite at pre-dose and 0.33, 0.66, 1, 2, 3, 4, 5, 12, 12.25, 12.5, 13, 14, 16, 18, 24 and 32h post morning dose
 
◆ MAD
 
Blood sampling for PK of IFB-088 and its metabolite at D1 and D14 pre-dose and 0.5, 1, 2, 3, 4, 6, 8, 10, 12, 13, 14, 17, 19 and 21h post morning dose; D2 24h post first dose just before the morning administration; D7 pre dose, 1h and 2 h post dose, D15 at 24, 30, 36 and 42h post D14 morning dose; D16 at 48h and 60h post D14 morning dose
 
Pharmacokinetic Assessments in urine
 
◆ SAD
 
Urine sampling for PK of IFB-088 and its metabolite IFB-139: Cohort 1: pre-dose and 0-4, 4-8, 8-16, 16-32 h post-dose intervals. From Cohort 2: pre-dose and 0-4, 4-8, 8-12, 12-24, 24-32h post-dose intervals
 
◆ MAD
 
Urine sampling for PK of IFB-088 and its metabolite: on D1 and D14: at pre-dose and 0-4, 4-12, 12-24 h post first dose; D6 at pre-dose, 0-4 and 4-12h; D15 at 24-36 and D16 at 36-48h post D14 morning dose
 
Biomarker assessments (exploratory)
 
There is currently no validated specific biomarker. So subjects will be asked to donate blood samples that could be used as healthy controls for research purposes in patients. A specific part in the informed consent will be signed. This assessment will be performed only for SAD part.
 
◆ SAD
 
Samples will be drawn at specific time points: Pre-dose, 1.5h and 24h post dose
 
• One sample (3 ml) on heparin lithium tube for PBMC extraction• One sample (2.5ml) on PAXgene tube for RNA extraction 
Samples will be stored in the CRB (Centre de Ressources Biologiques) at -150°C for 5 years after final database freeze and then destroyed.

--	---

	
◆ MAD
 
Sampling for biomarkers will not be performed during the MAD part.

Statistical methods
	
Data entry and statistical analysis will be performed under the responsibility of the CIC-CPCET Pharmacometrics unit.
 
The statistical software SAS® version 9.4 (SAS Institute Inc. Cary NC USA) will be used in statistical analysis.
 
Safety parameters
 
Laboratory results, vital signs measurements (blood pressure, heart rate, tympanic temperature), ECG parameters and VAS scores will be summarized using appropriate descriptive statistics. The incidence of all AEs and treatment-emergent AEs will be described by MedDRA® 21.0 or the latest available version at the study completion date (preferred term and system organ class).
 
PK parameters
 
The following parameters for IFB-088 and IFB-139 will be derived, where appropriate:
 
Plasma
 
 • Maximum observed plasma concentration (C_{max}), • Time of occurrence of C_{max} (T_{max}), • Terminal elimination rate constant (K_{el}), • Terminal half-life (t_{1/2}), • Area under plasma concentration-time curve from hour 0 to last sample with measurable plasma concentrations (AUC_{last}), • Area under plasma concentration-time curve from hour 0 to infinity (AUC_{0-∞}), • Apparent volume of distribution (V_d/F), • Apparent body clearance (CL/F), • Last measurable plasma concentration (C_{last}), • Time to reach last measurable plasma concentration (T_{last}) • Concentration at the end of a dosing interval before the next dose administration (C_{trough}), 
Urine
 
 • Maximum observed urine concentration (C_{maxU}), • Time of occurrence of C_{max} (t_{maxU}), • Area under urine concentration-time curve from hour 0 to last sample with measurable urine concentrations (AUC_{last}), • Area under urine concentration-time curve from hour 0 to infinity (AUC_{0-∞}), • Renal clearance (CL_r), • Total amount excreted in urine (A_e), • Percent of drug recovered in urine (A_e %dose). 
Pharmacokinetic modelling will be performed using a non-linear mixed effects model with NONMEM software (ICON Development Solutions v7.4). Data will be analysed using a first order conditional estimation method. The R software (www.r-project.org, v3.2.2) will be used for goodness-of-fit diagnostics and graphical displays.
 
Descriptive statistics and graphs will be performed for plasma and urine concentrations and PK parameters.


ABBREVIATIONS

AE	Adverse Event
ALT	Alanine aminotransferase (SGPT)
ANOVA	Analysis of Variance
AST	Aspartate aminotransferase (SGOT)
ATF4	Activating transcription factor 4
AUC	Area under concentration-time curve
AUC(0-∞)	Area under the concentration-time curve from time zero (pre-dose) extrapolated to infinite time
AUC(last)	Area under the concentration-time curve from time zero (pre-dose) to last time of quantifiable concentration within a subject across all treatments
AUC(0-24)	Area under the concentration-time curve from time zero (pre-dose) to 24 hour
BID	Twice a day
BMI	Body mass index
BP	Blood pressure
CI	Confidence Interval
CL/F	Apparent clearance following oral dosing
C _{max}	Maximum observed concentration
CMT	Charcot Marie Tooth
C _t	Last observed quantifiable concentration
CPK	Creatine phosphokinase
CRF	Case Report Form
CV	Coefficient of variance
DBP	Diastolic blood pressure
DEC	Dose Escalation Committee
DMP	Data Management Plan
DNA	Desoxyribonucleic acid
ECG	Electrocardiogram
EMA	European Medicine Agency
ER	Endoplasmic Reticulum
FDA	Food and Drug Administration
FIH	First in human
GCP	Good Clinical Practice

GFR	Glomerular Filtration Rate
GGT	Gamma glutamyltransferase
GLP	Good Laboratory Practice
GMP	Good Manufacturing Practice
HBsAg	Hepatitis B surface antigen
HIV	Human Immunodeficiency Virus
h	Hour(s)
HED	Human Equivalent Dose
hERG	Human Ether-à-go-go-Related Gene
HNPP	Hereditary neuropathy with liability to pressure palsies
HR	Heart rate
IB	Investigator's Brochure
ICH	International Conference on Harmonization of Technical Requirements for Registration of Pharmaceuticals for Human Use
IC ₅₀	Half maximal inhibitory concentration
IgM	Immunoglobulin M
IMP	Investigational Medicine Product
IMPD	Investigational Medicine Product Dossier
INR	International Normalized Ratio
IUD	Intrauterine device
Kg	Kilogram
L	Liter
LDH	Lactate Deshydrogenase
µg	Microgram
µL	Microliter
MAD	Multiple Ascending Dose
MPZ	Myelin Protein Zero
MPZS63del	Transgenic myelin protein zero S63del mouse model
MPZR98C/+	Heterozygous myelin protein zero R98C knock-in mouse model
MRSD	Maximum Recommended Starting Dose
MTD	Maximal Tolerated Dose
NOAEL	No Observed Adverse Effect Level

PK	Pharmacokinetic
PMP22	Peripheral myelin protein 22
PP1	Protein Phosphatase 1
PP/PPP1R15A	Stress-induced holophosphatase complex
PPP1R15A	Protein phosphatase 1 regulatory subunit 15A
PPP1R15B	Protein phosphatase 1 regulatory subunit 15B
QoL	Quality of Life
QTcB	QT duration corrected for heart rate by Bazett's formula
QTcF	QT duration corrected for heart rate by Fridericia's formula
RBC	Red blood cells
RNA	Ribonucleic acid
SAD	Single ascending dose
SAE	Serious adverse event(s)
SAP	Statistical Analysis Plan
SID	Once a day
SPM	Study Procedures Manual
TEAE	Treatment-emergent adverse event
Tlast	Time to reach last measurable plasma concentration
t _{1/2}	Terminal phase half-life
Tmax	Time of occurrence of C _{max}
ULN	Upper limit of normal
UPR	Unfolded Protein Response
VAS	Visual Analogic Scale
WBC	White blood cells
WT	Wild Type

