- Safety laboratory tests (hematology, coagulation, biochemistry) in fasting state, at Day 3, Day 6, Day 10 and Day 13,
- Urinalysis on Day 3, Day 6, Day 10 and Day 13,
- PK blood sampling in the morning at Day 7 pre-dose, then 1h and 2h post morning dose,
- PK urine sampling on Day 6: pre dose, 0-4h and 4-12h,
- AE monitoring.

6.5.4.4. *Day 14*

The following procedures will be performed at several time points (see Flow chart Section [3.5.3](#)):

- Study treatment dosing in 2 daily administrations separated by an interval of 12 hours,
- Vital signs (including tympanic body temperature) in the morning pre-dose,
- Diuresis monitoring,
- PK blood sampling,
- PK urine sampling,
- AE monitoring,

- Vigilance assessment at pre-dose, 1.5h post first dose and 12h post morning dose.

6.5.4.5. *Day 15 to Day 17*

The following procedures will be performed:

- Full physical exam at Day 17 before discharge,
- Vital signs every morning,
- Tympanic body temperature at Day 17,
- Safety laboratory tests (hematology, coagulation, biochemistry) in fasting state at Day 17,
- Urinalysis on Day 17,
- 12-lead ECG on Day 17,
- Diuresis monitoring on Day 15 and Day 16,
- PK blood sampling on Day 15 (17h, 19h, 21h, 24h, 30h, 36h and 42h post Day 14 morning dose) and on Day 16 (48h and 60h post Day 14 morning dose),
- PK urine sampling on Day 15 (end of collection of T12-24h and T24-36h post Day 14 morning dose) and on Day 16 (T36-48h post Day 14 morning dose),
- AE monitoring,
- Discharge after assessment of scheduled evaluations and medical authorization.

The subject will be asked to return for a follow-up visit, scheduled 7 to 14 days post last dose.

6.5.4.6. *Follow-up / End of study visit (7 to 14 days post last dose)*

The following procedures will be performed

- Vital signs measurement (including tympanic body temperature)
- Full physical examination,
- 12-lead ECG,
- Laboratory evaluation (hematology, coagulation, biochemistry and urinalysis),
- AE monitoring,
- Review of concomitant medications.

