Biochemistry, Hematology, Coagulation (5.5+2+2.7 mL)
Total = 10.2 mL
- Follow up visit
Biochemistry, Hematology, Coagulation (5.5+2+2.7 mL)
Total = 10.2 mL

Total on the overall duration of the study: 410.1 mL

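### In the MAD, the 50% creatinine-rise rule, read literally, lapses after Day 6, leaving only the 120 µmol/L limit as a numeric creatinine rule at the Day 10, 13 and 17 draws

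*Combined protocol and SAP*

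**What the plan says.** **Draw days.** The synopsis gives MAD "haematology, coagulation and biochemistry on D-1, D3, D6, D10 and D13 in the morning before dosing and D17 at discharge", plus follow-up. Section 6.5.4.3 agrees for the dosing period: safety bloods are taken "in fasting state, at Day 3, Day 6, Day 10 and Day 13". Section 6.7.2 itemises blood by visit and states "Total on the overall duration of the study: 410.1 mL". In the SAD the synopsis has "haematology, coagulation and biochemistry on D-1, D2 24h post dose and FU", so a 24 h draw exists there.

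**Renal rule.** Section 3.4.3.3 has three creatinine arms: above 120 µmol/L (1.2 × ULN); a change from baseline of at least 30 µmol/L in 24 h; and a change from baseline of at least 50% in a week. Appendix 2 words the last as at least 1.5 × baseline in 7 days. One subject meeting a criterion is withdrawn; two in a cohort bar further escalation. Haematuria and the urinary beta-2-microglobulin/creatinine ratio are further criteria.

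**Baseline.** Section 3.4.3.3 gives no definition of its own. Section 9.3.4 uses the last value before first dosing, which for creatinine is D-1.

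**Cardiovascular schedule.** After the pre-dose baseline, the synopsis lists MAD ECGs at "1, 2, 4, 8, 12h post first dose; D3, D6, D10 and D13 in the morning before dosing and D17 at discharge", so those on dosing days after D1 are all pre-dose. BP and heart rate are taken at 24 h on D2, then "every morning pre dose from D3 to D17; FU". For D14, section 6.5.4.4 lists "Vital signs (including tympanic body temperature) in the morning pre-dose" and no ECG, while the synopsis has temperature "on D14 at pre dose, and 1.5, 12h post dose".

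**The concern.** The kidney is the organ the protocol singles out. Section 1.3.2 describes drug-containing crystals in the renal tubules and commits to regular renal monitoring. Table 1 reports adverse renal findings in a 10-day rat study (10 mg/kg once daily) and a 14-day dog study (6 mg/kg once daily). Those are study lengths, so the time of onset is not known, but a lesion that builds up over 10 to 14 days would show mainly at the D10, D13 and D17 draws.

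A relative-rise rule is there to catch a subject who starts low in the normal range and loses function without crossing a fixed limit. If it lapses after D6, such a subject can keep dosing, and a cohort with two such subjects can escalate, without a numeric creatinine rule being met.

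**Working it through.** **1. Are the draw days complete?** The MAD flow chart (3.5.3) is not in the supplied text, so I checked the blood budget in 6.7.2.
- Screening: 18.7 mL.
- Safety bloods on D-1, D3, D6, D10, D13, D17 and follow-up: 7 × 10.2 = 71.4 mL.
- PK on D1, D2, D7, D14, D15, D16: 96 + 32 + 24 + 96 + 56 + 16 = 320 mL.
- Total: 18.7 + 71.4 + 320 = 410.1 mL, which reproduces the stated figure. There is no room for an unlisted creatinine draw.

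**2. Which draws fall within seven days?** There is no Day 0.

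| Draw | Days from D-1 | Days from D1 | Within 7 days? |
|---|---|---|---|
| D3 | 3 | 2 | yes |
| D6 | 6 | 5 | yes |
| D10 | 10 | 9 | no |
| D13 | 13 | 12 | no |
| D17 | 17 | 16 | no |

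The answer is the same from either origin: 3 of 5 scheduled draws are outside. For withdrawal from dosing the relevant count is 2 of 4 (D10 and D13), because D17 follows the last dose.

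**3. What does the 120 µmol/L limit catch on those days?** The implied ULN is 120/1.2 = 100 µmol/L. A 50% rise from baseline B exceeds 120 only if 1.5B > 120, that is B > 80. The rise needed to reach 120 is 120/B − 1.

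| Baseline (µmol/L) | 50% rise reaches | Rise needed to reach 120 |
|---|---|---|
| 60 | 90 | 100% |
| 70 | 105 | 71% |
| 75 | 112.5 | 60% |
| 80 | 120 | 50% |

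From a baseline of 70, values from 105 to 120 are a rise of at least 50% that meets no numeric creatinine rule at D10, D13 or D17.

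**4. Does a rolling seven-day reading rescue it?** Mostly. D10 can then be compared with D3 and D6, D13 with D6 and D10, and D17 with D10 and D13, so an abrupt rise is caught. A slow one is not. Constructed example: 70, 74, 82, 94, 106, 116 µmol/L on D-1, D3, D6, D10, D13, D17.
- Over the longest window available within seven days: D-1 to D6 82/70 = 1.17; D3 to D10 94/74 = 1.27; D6 to D13 106/82 = 1.29; D10 to D17 116/94 = 1.23. None reaches 1.5, and the maximum, 116, is below 120.
- Against D-1 with no limit: D10 94/70 = 1.34; D13 106/70 = 1.51; D17 116/70 = 1.66. The corrected rule fires at D13.

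**5. How much dosing is at stake?** After the D10 pre-dose draw, 5 days × 2 = 10 of 28 doses remain; after D13, 2 × 2 = 4.

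**6. How many subjects start below 80?** The documents do not say. Assuming a normal baseline with SD 8 to 12 µmol/L, P(B < 80) = Φ((80 − mean)/SD): 66-73% at mean 75, 50% at mean 80, 27-34% at mean 85.

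**7. Minor point.** On D2-D14 the synopsis and 6.5.4 list post-dose ECGs on 0 of 4 ECG days and post-dose BP/HR on 0 of 13 days. The stake is small. Table 8 expects a Cmax of 3.77 ng/ml at 50 mg, 3.77/23.77 = 16% of the stopping limit. Section 3.1.2 puts five half-lives within 36 h, so the half-life is at most 7.2 h and accumulation at most 1/(1 − 2^(−12/7.2)) = 1.46. That gives 3.77 × 1.46 = 5.50 ng/ml, or 23% of the limit.

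**The case against.** **Other protections remain.** This stands. Beta-2-microglobulin and haematuria are checked on the same MAD days, and the protocol regards the former as a sensitive marker of proximal tubular damage. Section 3.4.3 has a general rule on clinically significant drug-related laboratory abnormalities in two or more subjects, and treats clinically significant changes from baseline as a safety signal with no seven-day window. The dose escalation committee sees laboratory data before each step, and the investigator may withdraw anyone for safety. A reader might infer that renal stopping ends after D6; the documents do not support that. But these protections either measure something else or depend on judgement, and the safety-signal clause leads to closer review, not to withdrawal.

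**The gap depends on a literal reading.** Also fair. Section 3.4.3.3 cites an acute kidney injury definition, and an investigator might roll the window. The text ties the change to baseline, however, and slow creep escapes even when the window rolls.

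**The example is constructed, and the correction would stop it only at D13.** True: the saving there is 4 of 28 doses. A subject already 50% up at D10 would be spared 10.

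**The 24 h arm.** A reader might infer that it is a defect because no two scheduled MAD draws are within 24 h of each other. That does not follow. The renal section serves both parts, the arm fits the SAD 24 h draw, and in the MAD it works on unscheduled repeats.

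**The animal signal.** The 10- and 14-day findings came with once-daily dosing; the MAD is twice daily for that reason, and dogs at 12 mg/kg/day in two doses for 13 weeks showed no renal toxicity. In the 13-week rat study, males at 6 mg/kg/day had crystal nephropathy with a day-90 AUC of 23.6 ng/ml.h, against 25.57 and 42.62 expected in MAD cohorts 2 and 3. A reader might infer that the doses are unsafe. The documents do not support that: the durations differ, rat pharmacokinetics are non-linear, and the plan therefore sets its margins on dogs, where they are wide.

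**ECG and BP/HR.** A reader might infer that cardiac stopping rules are blind under repeated dosing. That is not secure: section 6 says exact times are in the flow charts, and the MAD chart is not in the supplied text. The visible texts already differ on D14 temperature. D1 and SAD post-dose readings exist, the SAD showed no accumulation at 24 h, and section 6 permits re-timing towards peak.

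**Conclusion.** The concern holds as a mismatch between the time limit of one creatinine arm and the MAD draw days. On the literal reading the 50% arm covers 2 of 5 scheduled draws; at D10 and D13 for withdrawal, and at D17 for escalation, a 50% rise from a baseline below 80 µmol/L meets no numeric creatinine rule. On a rolling reading only gradual rises are missed. The result rests on D-1 being the baseline (9.3.4) and on the flow chart agreeing with the synopsis, 6.5.4.3 and 6.7.2, which agree with one another. How many subjects are affected depends on baseline creatinine, which the documents do not give.

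The gap is moderate because of the remaining renal safeguards, but it should be closed: it sits in a stated withdrawal and escalation rule for the main target organ. The ECG and BP/HR point is minor and provisional.

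**What to change.** In section 3.4.3.3 and Appendix 2, state that in the MAD a creatinine rise of at least 50% over the D-1 value counts at every scheduled draw (D3, D6, D10, D13, D17), with no seven-day limit. Leave the 24 h arm unchanged, for the SAD 24 h draw and for unscheduled repeats. The cost is slightly more withdrawals or escalation reviews, and no extra blood.

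Optional, after checking flow chart 3.5.3: one ECG with BP/HR on D14 at 1 h or 2 h after the morning dose, whichever is nearer the SAD Tmax. Both are already D14 PK times. At 2 h, take the readings before breakfast, which is served then. The cost is one ECG and one BP/HR reading; the D13 ECG could be moved to D14 instead, at the price of one trough reading.
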